### 7.4.1 Administration of Study Therapy

For details on the dosing schedule per protocol, see [Section 2.1](#).

The following parameters will be summarized (descriptive statistics) by treatment group:

- Number of cycles received (summary statistics).
- Duration of treatment
  - using a KM curve whereby the last dose date will be the event date for those subjects who are off study therapy. Subjects who are still on study therapy will be censored on their last dose date. Median duration of treatment and associated 95% CI will be provided.

The following parameters will be summarized (descriptive statistics) by study therapy and treatment group:

- Relative dose intensity (%) using the following categories:  $< 50\%$ ;  $50 - < 70\%$ ;  $70 - < 90\%$ ;  $90 - < 110\%$ ;  $\geq 110\%$ .
- Cumulative dose

A by-subject listing of dosing of study medication (record of study medication, infusion details, dose change).

Key parameters used to characterize dosing data for the nivo+ipi arm are defined in [Table 7.4.1-1](#); for subjects treated with XELOX in the nivo+chemo and chemotherapy arms in [Table 7.4.1-3](#); for subjects treated with FOLFOX in the N+C and chemotherapy arms in [Table 7.4.1-5](#).

**Table 7.4.1-1: Administration of Study Therapy in the Nivolumab plus Ipilimumab Arm**

	Nivolumab	Ipilimumab
Dosing schedule per protocol	1mg/kg Q3Wx4 then 240mg Q2W, IV Or 240mg Q2W, IV or 480 Q4W, IV	3mg/kg Q3W, IV
Dose*	Total dose administered (mg)/most recent weight (kg) Or Total dose administered (mg)	Total dose administered (mg)/most recent weight (kg)
Cumulative Dose	The sum of all doses (mg) administered to a subject during the treatment period	The sum of all doses (mg/kg) administered to a subject during the treatment period
Relative Dose Intensity (%)	See equation in Table 7.4.1-2	$100 \times [\text{Cum dose (mg/kg)} / [(\text{Last ipilimumab dose date in the nivo-plus-ipi phase} - \text{ipilimumab Start dose date} + 21) \times 3 / 21]]$
Duration of Treatment	Last dose date (of the last administered study therapy) - Start dose date (of the first administered study therapy) + 1	

\* Dose administered in mg at each dosing date and weight are collected on the CRF

**Table 7.4.1-2: Formula for Relative Dose Intensity for Nivolumab in Nivolumab plus Ipilimumab Regimen**

Overall duration of Nivo treatment	(last dose date of nivo - start dose date of nivo + X) X= 14 days if last dose is 240 mg X= 21 days if last dose is 360 mg (some patients take 360 mg despite protocol instruction) X= 28 days if last dose is 480 mg
Overall RDI*	<math>w_1 * RDI_1 + (1 - w_1) * RDI_2</math>
RDI1	100 x [Cum dose (mg/kg) in nivo-plus-ipi phase / [(Last nivolumab dose date in the nivo-plus-ipi phase – nivolumab Start dose date + X) x 1 / 21]]
RDI2	<math>100 \times \frac{\text{cumulative dose in mono phase (mg)}}{\left\{ \left[ (\text{nivo last dose date in mono phase} - \text{start date in the nivo mono phase} + X) \times \frac{120}{7} \right] \right\}}</math> X as above
w1	<math>[(\text{First nivolumab dose date in the mono phase} - \text{nivolumab Start dose date in nivo-plus-ipi phase}) / \text{overall duration of Nivo treatment}]</math>

\* if patient did not start the combo phase then overall RDI= RDI1

**Table 7.4.1-3: Administration of Study Therapy for Subjects Treated with XELOX**

	Nivolumab	Oxaliplatin	Capecitabine
Dosing schedule per protocol	360mg Q3WK, IV or 480 mg Q4WK, IV (nivo mono)	130mg/m  Q3WK, IV	1000mg/m  twice daily D1-14, Q3WK, oral
Dose*	Total dose administered (mg)	Total dose administered (mg) / most recent BSA	Total dose administered (mg) / most recent BSA
Cumulative Dose	The sum of all doses (mg) administered to a subject during the treatment period	The sum of all doses (mg/m  ) administered to a subject during the treatment period	The sum of all doses (mg/m  ) administered to a subject during the treatment period

**Table 7.4.1-3: Administration of Study Therapy for Subjects Treated with XELOX**

	Nivolumab	Oxaliplatin	Capecitabine
Relative Dose Intensity (%)	see formula in Table 7.4.1-4	$100 \times [\text{Cumulative dose (mg/m}^2) / [\text{Last oxaliplatin dose date} - \text{oxaliplatin Start dose date} + 21) \times 130/21]]$	$100 \times [\text{Cumulative dose (mg/m}^2) / [\text{First dose of capecitabine in the last cycle} - \text{capecitabine Start dose date} + 21) \times 28000/21]]$
Duration of Treatment	Last dose date (of the last administered study therapy) - Start dose date (of the first administered study therapy) + 1		

\* Dose administered in mg at each dosing date and BSA (computed using recent weight and baseline height) are collected on the CRF.

**Table 7.4.1-4: Formula for Relative Dose Intensity for Nivolumab in Nivolumab plus XELOX Regimen:**

$$100 \times \frac{\text{cumulative dose (mg)}}{\left[ \begin{aligned} &[(\text{last dose date of nivo 360 mg} - \text{start date of nivo} + 21) \times \frac{360}{21}] \\ &+ [(\text{last dose date of nivo 480 mg} - \text{start date of nivo 480mg} + 28) \times \frac{480}{28}] \end{aligned} \right]}$$

**Table 7.4.1-5: Administration of Study Therapy for Subjects Treated with FOLFOX**

	Nivolumab	Oxaliplatin	Leucovorin	Fluorouracil
Dosing schedule per protocol	240mg Q2WK, IV or 480 mg Q4WK, IV (nivo mono)	85mg/m  Q2WK	400mg/m  Q2WK	Bolus 5-FU: 400mg/m  Q2WK, IV on Day 1 of the cycle  Continuous 5-FU: 1200mg/m  Q2WK, IV continuous infusion on Day1-2 of the cycle
Dose*	Total dose administered (mg)	Total dose administered (mg) / most recent BSA	Total dose administered (mg) / most recent BSA	Total dose administered (mg) / most recent BSA

**Table 7.4.1-5: Administration of Study Therapy for Subjects Treated with FOLFOX**

	Nivolumab	Oxaliplatin	Leucovorin	Fluorouracil
Cumulative Dose	The sum of all doses (mg) administered to a subject during the treatment period	The sum of all doses (mg/m  ) administered to a subject during the treatment period	The sum of all doses (mg/m  ) administered to a subject during the treatment period	The sum of all doses (mg/m  ) administered to a subject during the treatment period
Relative Dose Intensity (%)	See formula in Table 7.4.1-6	100 x [Cumulative dose (mg/m  ) / [Last oxaliplatin dose date – oxaliplatin Start dose date + 14) x 85/14]]	100 x [Cumulative dose (mg/m  ) / [Last leucovorin dose date – leucovorin Start dose date + 14) x 400/14]]	Bolus 5-FU: 100 x [Cumulative dose (mg/m  ) / [First dose of fluorouracil in the last cycle – fluorouracil Start dose date + 14) x 400/14]]  Continuous 5-FU: 100 x [Cumulative dose (mg/m  ) / [First dose of continuous fluorouracil in the last cycle – continuous fluorouracil Start dose date + 14) x 2400 / 14]]
Duration of Treatment	Last dose date (of the last administered study therapy) - Start dose date (of the first administered study therapy) + 1			

\* Dose administered in mg at each dosing date and BSA (computed using recent weight and baseline height) are collected on the CRF.

**Table 7.4.1-6: Formula for Relative Dose Intensity for Nivolumab Nivolumab plus FOLFOX Regimen**

---

---

$$100 \times \frac{\text{cumulative dose (mg)}}{\left\{ \begin{aligned} & \left[ (\text{last dose date of nivo 240 mg} - \text{start date in the nivo mono phase} + 14) \times \frac{240}{14} \right] \\ & + \left[ (\text{last dose date of nivo 480 mg} - \text{start date of nivo 480mg} + 28) \times \frac{480}{28} \right] \end{aligned} \right\}}$$

---

---

## 7.4.2 Modification of Study Therapy

### 7.4.2.1 Dose Delays

A dose will be considered as actually delayed if the delay is exceeding the number of days in Table 7.4.2.1-1.

**Table 7.4.2.1-1: Dose Delays**

	Ipilimumab	Q3W Nivolumab (a)	Q2W Nivolumab (b)	Q4W Nivolumab (c)	XELOX (d)	FOLFOX (d)
Specifications per Protocol						
Dose considered as actually delayed	If the delay is exceeding 3 days	If the delay is exceeding 3 days	If the delay is exceeding 2 days	If the delay is exceeding 3 days	If the delay is exceeding 3 days	If the delay is exceeding 2 days
Maximum delay allowed between doses	42 days	42 days	42 days	42 days	Not specified	Not specified
Definitions for the Analysis						
Dose Delay	duration of preceding cycle in days – 21	duration of preceding cycle in days – 21	duration of preceding cycle in days – 14	duration of preceding cycle in days – 28	duration of preceding cycle in days – 21	duration of preceding cycle in days – 14
Categories of dose delays	on-time, 4 - 7 days, 8 - 14 days, 15 - 42 days, > 42 days	on-time, 4 - 7 days, 8 - 14 days, 15 - 42 days, > 42 days	on-time, 3 - 4 days, 5 - 7 days, 8 - 14 days, 15 - 42 days, > 42 days	on-time, 4 - 7 days, 8 - 14 days, 15 - 42 days, > 42 days	on-time, 4 - 7 days, 8 - 14 days, 15 - 42 days, > 42 days	on-time, 3 - 4 days, 5 - 7 days, 8 - 14 days, 15 - 42 days, > 42 days
(a) nivo-plus-ipi phase in the nivo+ipi arm, FOLFOX-treated subjects in the nivo+chemo arm (b) nivo mono phase in the nivo+ipi arm, XELOX-treated subjects in the nivo+chemo arm (c) applicable to all arms with nivolumab, when nivolumab administered alone after treatment with nivolumab in combination with ipilimumab, FOLFOX or XELOX. (d) in the nivo+chemo and in the chemotherapy arms						

The following parameters will be summarized by study therapy and treatment group:

- Number of subjects with at least one dose delayed, the number of doses delayed per subject, the reason for dose delay and the length of dose delay.

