4.5.1.1 Nivolumab and Ipilimumab Dose and Schedule

Subjects randomized to the nivolumab-plus-ipilimumab arm should receive nivolumab 1 mg/kg administered IV over 30 minutes followed by ipilimumab 3 mg/kg administered IV over 30 minutes on Day 1 of each treatment cycle every 3 weeks for 4 doses (Cycles 1 to 4), followed by nivolumab 240 mg administered IV over 30 minutes on Day 1 of each treatment cycle every 2 weeks (Cycle 5 and beyond) until PD (unless treatment beyond PD is permitted; see Section 4.5.1.6), unacceptable toxicity, withdrawal of consent, or the study ends, whichever occurs first. Subjects should begin study treatment within 3 calendar days of randomization. See Table 4.5.1.1-1 for details on the dosing schedule of nivolumab and ipilimumab. From Amendment 29, subjects treated in the nivolumab 240 mg Q2W have an option to switch nivolumab 480 mg Q4W, the nivolumab 480 mg should be given 2 weeks following the last administration of nivolumab 240 mg dose.

Table 4.5.1.1-1: Dose Schedule of Nivolumab and Ipilimumab						
Treatment Group	Drug Name	Cycle 1 (Week 1)	Cycle 2 (Week 4) ^a	Cycle 3 (Week 7) ^a	Cycle 4 (Week 10) ^a	Cycle 5 (Week13) till EOT (Q2 weeks) ^b
Nivolumab +Ipilimumab	Nivolumab 1 mg/kg	Day 1	Day 1	Day 1	Day 1	-
	Ipilimumab 3 mg/kg	Day 1	Day 1	Day 1	Day 1	-
Nivolumab	Nivolumab 240 mg	-	-	-	-	Day 1

^a Cycles 2 to 4: Subsequent nivolumab and ipilimumab doses may be administered within 3 days before or after the scheduled date if necessary. Subjects may be dosed no less than 18 days between doses.

Dosing calculations should be based on the body weight assessed at baseline. It is not necessary to re-calculate subsequent doses if the subject weight is within 10% of the weight used to calculate the previous dose. All doses should be rounded to the nearest milligram per institutional standard.

b Cycle 5 till EOT: Nivolumab may be administered up to 2 days before or 3 days after the scheduled date if necessary. Subjects may be dosed no less than 12 days between doses.

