**Figure 2.1-1: Study Scheme**

\* Nivolumab + Ipilimumab arm is closed to enrollment as of 05-June-2018.

The accrual was complete in May 2019 and the sample size is 2031 subjects randomized, with 83 subjects randomized in 1:1 ratio to nivo + ipi vs. chemo, followed by ~1098 subjects randomized in 1:1:1 ratio to the 3 arms until the closure of enrollment of the nivo+ipi arm, and finally 850 subjects randomized to nivo+chemo vs. chemo (see also Table 5.1-1).

The treatment administration is as follows:

- **Nivo+Ipi Arm:** nivolumab 1mg/kg administered IV over 30 minutes followed by ipilimumab 3mg/kg administered IV over 30 minutes on Day 1 of each treatment cycle every 3 weeks for 4 doses (Cycles 1 to 4), followed by nivolumab 240mg administered IV over 30 minutes on Day 1 of each treatment cycle every 2 weeks (Cycle 5 and beyond)

Subjects treated in the nivolumab 240mg Q2W have an option to switch nivolumab 480mg Q4W, the nivolumab 480mg should be given 2 weeks following the last administration of nivolumab 240 mg dose.

- Nivo+Chemo Arm (XELOX or FOLFOX):
  - Nivolumab plus XELOX:
    - ◆ Nivolumab 360mg IV over 30 minutes on Day 1 of each treatment cycle, every 3 weeks
    - ◆ Oxaliplatin 130mg/m^2 IV on Day 1 of each treatment cycle + capecitabine 1000mg/m^2 orally twice daily on Days 1 to 14 of each treatment cycle, every 3 weeks
  - Nivolumab plus FOLFOX:
    - ◆ Nivolumab 240mg IV over 30 minutes on Day 1 of each treatment cycle, every 2 weeks
    - ◆ Oxaliplatin 85mg/m^2 + leucovorin 400mg/m^2 + fluorouracil 400mg/m^2 IV on Day 1 of each treatment cycle, and fluorouracil 1200 mg/m^2 IV continuous infusion over 24 hours daily or per local standard on Days 1 and 2 of each treatment cycle, every 2 weeks

Nivolumab 480mg Q4W is permitted when all chemotherapy components are discontinued and nivolumab is continued alone. Subjects must be in the study for a minimum of 6 months from Cycle 1, Day 1 before switching to 480mg Q4W nivolumab. Nivolumab 480mg should be given 2 weeks or 3 weeks following the last administration of nivolumab 240mg Q2W or 360mg Q3W, respectively.

- Chemo Arm (XELOX or FOLFOX):
  - XELOX: Oxaliplatin 130mg/m^2 IV on Day 1 of each treatment cycle + capecitabine 1000mg/m^2 orally twice daily on Days 1 to 14 of each treatment cycle, every 3 weeks

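### The SAP's nivolumab dose-delay and relative-dose-intensity derivations give wrong or undefined results for subjects dosed exactly on schedule

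*SAP*

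**What the plan says.** **Schedule.** SAP Section 2.1 gives nivolumab with XELOX as "Nivolumab 360mg IV over 30 minutes on Day 1 of each treatment cycle, every 3 weeks", and with FOLFOX as "Nivolumab 240mg IV over 30 minutes on Day 1 of each treatment cycle, every 2 weeks". Protocol Section 4.5.2.1 and SAP Tables 7.4.1-3 and 7.4.1-5 agree.

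**Dose delay (SAP Table 7.4.2.1-1).** The Q3W nivolumab column takes the preceding cycle length minus 21 and calls a dose delayed beyond 3 days. The Q2W column takes "duration of preceding cycle in days – 14" and calls a dose delayed beyond 2 days. Footnote (a) says who belongs in the Q3W column and footnote (b) who belongs in the Q2W column. From the second part of (a) they read "FOLFOX-treated subjects in the nivo+chemo arm (b) nivo mono phase in the nivo+ipi arm, XELOX-treated subjects in the nivo+chemo arm".

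**RDI with FOLFOX (Table 7.4.1-6).** The numerator is the cumulative nivolumab dose, which Table 7.4.1-5 defines over the whole treatment period. The 240 mg term of the denominator runs from the "start date in the nivo mono phase". The parallel XELOX formula (Table 7.4.1-4) runs from the "start date of nivo".

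**RDI with ipilimumab (Table 7.4.1-2).** RDI1 covers the combination phase and RDI2 the phase on nivolumab alone. The overall RDI weights them by w1, which needs the date of the first mono-phase dose. RDI1 adds X days to the combination-phase duration. X is 14, 21 or 28 according to whether the last dose was 240, 360 or 480 mg. A footnote adds "if patient did not start the combo phase then overall RDI" equals RDI1.

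**Dosing window.** Table 7.4.2.1-1 places the 2-day Q2W threshold among the protocol specifications. Protocol Section 4.5.1.1 states "Nivolumab may be administered up to 2 days before or 3 days after the scheduled date if necessary", and Protocol Table 5.1-3 gives the same window for nivolumab with FOLFOX.

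**The concern.** The footnotes reverse the two backbones, so each group would be judged against the other group's interval. The FOLFOX RDI sets a whole-treatment dose against part of the treatment time. The combination-phase RDI uses an interval that belongs to a different phase, and it has no value for subjects who never leave the combination phase. The footnote that ought to cover those subjects names the wrong phase.

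Dose delay and RDI are planned outputs, reported by study therapy and treatment group, and they inform how well nivolumab could be delivered with each partner. The errors run in different directions for XELOX and FOLFOX, so the contrast between backbones is distorted as well as the levels. Version 5.0 of the SAP changed the RDI formula for the nivolumab plus ipilimumab arm specifically so that an overall RDI could be reported.

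**Working it through.** The plan states no numerical delay or RDI result, so there is no figure to reproduce. The check applies each printed rule to hypothetical subjects dosed exactly on schedule, who should show a delay of 0 and an RDI of 100%.

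**Control: XELOX formula (Table 7.4.1-4).**
- Ten doses of 360 mg: 3600 / [(9×21 + 21) × 360/21] = 3600/3600 = 100%.
- Six further doses of 480 mg: 6480 / (3600 + 2880) = 100%.

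This formula is right and the set-up is sound.

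**1. Dose delay as footnoted.**
- XELOX read in the Q2W column: an on-time 21-day cycle gives 21 − 14 = 7 days, in the 5–7 day category. The shortest interval that Protocol Table 5.1-3 allows with XELOX is 18 days, which gives 18 − 14 = 4, still above 2. No permitted XELOX interval can be on time.
- FOLFOX read in the Q3W column: an on-time 14-day cycle gives 14 − 21 = −7. A 24-day cycle, truly 24 − 14 = 10 days late, gives 24 − 21 = 3 and counts as on time. A 25-day cycle, 11 days late, gives 4 and falls in the 4–7 day category.
- With the backbones exchanged, both on-schedule cases give 0.
- The same table's chemotherapy columns subtract 21 for XELOX and 14 for FOLFOX. A XELOX subject given both drugs on the same on-time day would be on time for XELOX and 7 days late for nivolumab.

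**2. FOLFOX RDI (Table 7.4.1-6), taking the mono phase to start at the first dose of nivolumab alone.**
- 26 doses of 240 mg with FOLFOX, then 13 alone: 39×240 / [(12×14 + 14) × 240/14] = 9360/3120 = 300%.
- 26 doses of 240 mg, then a direct switch to six of 480 mg: the first 480 mg dose comes 14 days after the last 240 mg dose, so the 240 mg term is (−14 + 14) × 240/14 = 0. The 480 mg term is (5×28 + 28) × 480/28 = 2880. RDI = (6240 + 2880)/2880 = 9120/2880 = 317%.
- No phase on nivolumab alone: the start date does not exist and RDI cannot be computed.
- Counted from the first nivolumab dose, each of these gives 100%.

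Other on-schedule mixes range from 136% (13 doses of 240 mg, then 18 of 480 mg: 11760/8640) to 400% (12 with FOLFOX, then 4 alone at 240 mg: 3840/960).

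**3. Nivolumab plus ipilimumab, RDI1 (Table 7.4.1-2).** With k on-schedule doses of 1 mg/kg, RDI1 = 100 × k / [((k − 1)×21 + X)/21].

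| Combination doses | X = 14 | X = 21 | X = 28 |
|---|---|---|---|
| 1 | 150% | 100% | 75% |
| 4 | 84/77 = 109.1% | 84/84 = 100% | 84/91 = 92.3% |

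- Overall RDI after 4 combination and 20 mono doses of 240 mg: w1 = 84/364 = 0.231, so 0.231×109.1 + 0.769×100 = 102.1%. After 4 and 1: w1 = 84/98 = 0.857, giving 107.8%.
- A subject who stops during the combination has a last dose of 1 mg/kg, for which X is not defined. There is also no mono-phase date for w1.
- Size of that group, on the SAP's planning assumption only: the first mono dose is due at Week 13, 84 days after the first dose, or 84/30.4375 = 2.76 months. At the assumed hazard of 0.099 per month (Table 5.2.2-1), 1 − exp(−0.099×2.76) = about 24% would have died by then, before counting other discontinuations.

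**4. Footnote to Table 7.4.1-2.** A subject without a combination phase is sent to RDI1, the combination-phase term, which that subject does not have.

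**5. Q2W threshold.** A dose exactly 3 days late is inside the protocol window but is counted as delayed.

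**The case against.** The strongest reply concerns reach.

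- The start-date error is confined to the FOLFOX formula and the interval error to RDI1; the XELOX formula and RDI2 are correct. This stands.
- The 300% and 317% are constructed cases and depend on how much nivolumab was given before and after FOLFOX stopped. This stands, and they are offered only as illustrations.
- After four combination doses, 109% and 92% both stay in the SAP's 90 to under 110% category, and the weighted overall values of 102% to 108% are close to 100%. This stands for those examples. It does not help subjects with fewer combination doses or with no defined value. Taking X from the last combination-phase dose instead does not help either, because that dose is 1 mg/kg and X then has no value for anyone.
- The footnote to Table 7.4.1-2 could also be repaired by sending subjects without a combination phase to RDI2. That would be consistent, but the arm begins with combination dosing, so the group needing a rule is the one that never reaches the mono phase. Either way the printed sentence is wrong.
- The 2-day threshold can be read as an analysis convention, and it affects only doses exactly 3 days late. The point is small; the mismatch with the protocol window remains.
- Exposure is also described by cycles, duration and cumulative dose. Adverse events leading to delay come from the case report form, not from this table. No endpoint or alpha depends on these derivations. All of this stands.
- Programmers may have used the correct intervals, which appear elsewhere in the SAP. The documents do not show how the tables were coded, and nothing in them corrects the footnotes or formulas.

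**Conclusion.** The derivations are wrong as written. The reversed footnotes give every protocol-compliant XELOX interval a nivolumab delay and hide FOLFOX delays of up to 10 days. The FOLFOX RDI is inflated for subjects who continue on nivolumab alone (136% to 400% in the on-schedule cases tried) and missing for those who do not. For nivolumab plus ipilimumab the bias after four combination doses is modest once weighted (about 102% to 108% in the cases with a last dose of 240 mg). The larger defect there is that subjects who stop in the combination phase have no defined RDI. The Q2W threshold is a minor inconsistency.

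These sizes assume that the rules are coded literally and that dosing is on schedule. The consequences are limited to descriptive exposure summaries. The errors should be corrected, but they do not touch the efficacy conclusions.

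**What to change.** 1. In Table 7.4.2.1-1, exchange XELOX and FOLFOX in footnotes (a) and (b).
2. In Table 7.4.1-6, count the 240 mg term from the first nivolumab dose, as Table 7.4.1-4 already does for 360 mg.
3. In Table 7.4.1-2, replace X in RDI1 by a fixed 21 days; keep X in RDI2 and in the overall duration.
4. Reword the footnote to Table 7.4.1-2 so that a subject who never starts the mono phase takes RDI1 as the overall value.
5. Reconcile the Q2W delay threshold with the protocol's dosing window, or label it as an analysis convention and not a protocol specification.
6. Compare the exposure programs with the corrected tables. The version 5.0 entry in the SAP's document history says that the nivolumab plus chemotherapy report was already written, so check its nivolumab delay and RDI tables and rerun them if the printed rules were used.

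The cost is a few words in the SAP, a programming check and possibly a rerun of descriptive tables. No dosing rule, data collection or efficacy analysis changes.

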### 7.4.2.2 Infusion Interruptions and Rate Changes

Each study therapy given as infusion can be interrupted and/or the IV infusion rate can be reduced. This information will be retrieved from CRF dosing pages.

For capecitabine, which is oral, interruption will be programmatically derived.

The following parameters will be summarized by study therapy and treatment group:

- Number of subjects with at least one dose infusion interruption, the reason for interruption, and the number of infusion interruptions per subject.
- Number of subjects with at least one IV infusion rate reduction, the reason for reduction and the number of infusion with IV rate reduction per subject (not for capecitabine).

